## 1.0 BACKGROUND AND RATIONALE

### 1.1 Study Synopsis

This is a single-arm pilot study to evaluate the feasibility and acceptability of a novel psychosocial intervention for parents with advanced cancer and their co-parents. In this single-center study, we will recruit ten mothers with metastatic breast cancer and their co-parents as dyads (N=20) to participate in the Fathers and Mothers Invested in the Lives of their Youth (FAMILY) intervention. The FAMILY intervention consists of manualized visits with a trained intervention facilitator and psychoeducation materials to help parents cope with cancer-related parenting concerns. The purpose of the intervention is to improve parenting concerns, emotional well-being, and end-of-life (EOL) preparation among participants. The primary hypothesis being tested is that a psychosocial intervention to reduce psychological distress and improve EOL preparation for mothers with metastatic breast cancer and their co-parents can be acceptable to the target population.

### 1.2 Background

**Cancer is the leading disease-specific cause of early parental death** in the United States (US), and one in five cancer patients is between the ages of 21 and 55, the prime parenting years. Among women, breast cancer is the leading cause of death from cancer globally, including women under age 50.

**Having dependent children worsens suffering for parents with advanced cancer and their families.** In addition to the physical symptoms, functional limitations, and spiritual distress caused by the disease, parents with advanced cancer experience extraordinary psychological suffering related to parenting. They have concerns about the impact of their illness and death on their children, as well as profound anticipatory grief about their inability to see their children into adulthood. Compared to advanced cancer patients without dependent children, parents are five times more likely to have anxiety. Co-parents—spouses, grandparents, or other adults who will assume caregiving responsibilities if the patient is unavailable—must cope with their own grief and fears about solo parenting. Cross-sectional studies demonstrate that nearly 60% of parents and co-parents meet screening threshold criteria for anxiety and depression respectively. The consequences of bereaved co-parent maladjustment are compelling—they are four times more likely than other caregivers to meet diagnostic criteria for major depressive disorder and generalized anxiety disorder, and their untreated depression is associated with worsened physical health and psychiatric disorders in their children. Children of seriously ill and dying cancer patients are twice as likely to experience clinically significant depressive symptoms and remain at risk for other long-term psychological effects including anxiety, academic difficulties, and suicidal ideation. The impact of terminal parental cancer and eventual death has lingering and long-term impact on the family.

**For parents with advanced cancer, psychological distress and lack of EOL preparation are interlinked.** In our research with bereaved fathers, reports of maternal worry about children were ubiquitous at the EOL and less than half of dying mothers were described as being at peace with dying. Many mothers were also inadequately prepared for the EOL—60% did not say

goodbye to their children prior to death and 50% did not die in the location of their choice. These outcomes mirror results from the Coping with Cancer prospective cohort study. Compared to advanced cancer patients without dependent children, parents were half as likely to be peaceful, had worse quality of life (QOL) at the EOL, and were half as likely to complete advance care directives. Together, these studies suggest that two defining features of the advanced cancer experience for parents are psychological suffering and inadequate EOL preparation.

**No psychosocial interventions are proven to improve psychological distress for parents with advanced cancer.** Much of the extant literature on cancer and parenting focuses on the effects of parental illness on children and heavily relies upon samples of early-stage cancer patients with high 5-year survival rates. Existing psychosocial interventions for parents with cancer are not specific to advanced cancer, lack formal intervention testing with a control group, or focus on pediatric, but not parental outcomes. Despite strong evidence that parents with advanced cancer experience extreme suffering, no therapeutic interventions are proven to address their unique needs.

**Parents with advanced cancer and their co-parents need tailored dyadic interventions.** First, most parents' overarching goal—the well-being of their children—requires planning for future parenting, but is not addressed in standard advance care planning or psychosocial interventions for patients with advanced cancer. Second, our preliminary data on co-parent strain emphasize the need for interventions for both the co-parent and patient. Third, the unique and high psychological distress in patients and co-parents may prevent their future EOL and childcare planning. Hence, they need customized strategies to reduce their distress. Fourth, interventions are more likely to be successful if patient and co-parent are targeted together by design due to the interdependence of experiences and psychological adjustment within dyads.

**Conceptual framework for the focus on dyads.** Lewis' Integrated Framework for Communal Coping & Interdependences proposes that individual members of a dyad influence each other's motivation (interdependence) and decision-making (coping) for health-related behavior change. A dyadic intervention should facilitate both greater intent and actual behavioral change for individuals by increasing the dyad's understanding of the mutuality of the problem. This model emphasizes interrelated psychological processes among dyads facing a health stressor by accounting for individual characteristics (e.g. demographic and illness factors), intrapersonal influences (e.g. individual appraisal and coping processes), and interpersonal characteristics (i.e. the simultaneous experiences of patient and co-parent and their influence on one another) on health outcomes. In this model, dyads experience a shared stressor (metastatic cancer), one parent's distress and readiness for EOL preparation will influence the other, and both parents will experience greater motivation to engage in EOL preparation by understanding their parenting concerns as mutual. In doing so, such a model facilitates more effective communication about their family's future care needs and reduces parental psychological distress (see Figure 1 for outcomes targeted by the intervention).

**Rationale for focus on mothers with metastatic breast cancer and their co-parents.** We focus on mothers with breast cancer due to high disease prevalence, evidence of willingness to

participate in psychosocial interventions, and reduced variability in intervention efficacy due to gender or disease differences.

### **1.3 Purpose and Rationale**

This study will evaluate whether a psychosocial intervention to reduce psychological distress and improve EOL preparation for mothers with metastatic breast cancer and their co-parents can be acceptable, feasible, and relevant to the target patient population.

This study is needed in order to generate critical data to: (1) refine the intervention in preparation for a pilot efficacy randomized controlled trial (RCT); and to generate preliminary data demonstrating the feasibility and acceptability of core intervention components. The preliminary data will support future grant applications for a full-scale efficacy RCT.

## **2.0 STUDY OBJECTIVES AND ENDPOINTS**

### **2.1 Primary Objective**

The primary objective of this study is to evaluate the acceptability of a pilot psychosocial intervention for mothers with metastatic breast cancer and their co-parents. Qualitative methods will evaluate acceptability based on patient and co-parent post-study satisfaction ratings and interviews.

### **2.2 Secondary Objectives**

- (1) A secondary objective of this study is to evaluate the feasibility of study procedures in preparation for a future RCT of the intervention. We will use interview data and descriptive statistics to evaluate and then refine screening, recruitment, retention, and intervention fidelity to optimally position us to conduct a RCT.
- (2) A secondary objective of this study is to explore the impact of the intervention on target outcomes of emotional well-being and parenting concerns in women with metastatic breast cancer.

## **3.0 PATIENT ELIGIBILITY**

### **3.1 Inclusion Criteria**

Participants who are patients must meet all of the inclusion criteria to participate in this study:

- 3.1.1. Be a woman with metastatic (stage IV) breast cancer who has current evidence of disease, and : (1) has previously received chemotherapy for metastatic disease, or (2) is unable to receive chemotherapy due to poor performance status
- 3.1.2. A mother of at least one dependent child, defined as a child <18 years of age who lives at least half-time in the home;
- 3.1.3. Be at least 18 years of age;

- 3.1.4. Adequate stamina to complete at least two study visits
- 3.1.5. Able to provide informed consent
- 3.1.6. Able to complete all study measures and visits in English;
- 3.1.7. Be willing to participate in study visits at the North Carolina Cancer Hospital (NCCH) if they live >75 miles away from NCCH or be willing to participate in study visits via virtual methods if UNC-CH COVID-19 precautions discourage in-person study visits;
- 3.1.8. Have an identified co-parent who is eligible and willing to participate in the study.

Eligible co-parent participants must meet all of the inclusion criteria to participate in the study:

- 3.1.9. Be an adult man or woman who is both a romantic partner or spouse of the patient and who would serve as the child(ren)'s primary caregiver if the patient were to become unavailable;
- 3.1.10. Able to provide informed consent;
- 3.1.11. Able to complete all study measures and visits in English;
- 3.1.12. Stated willingness to comply with all study procedures; and
- 3.1.13. Be at least 18 years of age.

### **3.2 Exclusion Criteria**

All participants meeting any of the exclusion criteria at baseline will be excluded from study participation:

- 3.2.1. Unable to participate in study visits due to illiteracy, inability to speak English or other causes.
- 3.2.2. Live more than 75-miles away from the North Carolina Cancer Hospital (NCCH) and unable to attend study visits at NCCH or unwillingness to participate in virtual visits during UNC-CH mandated COVID-19 precautions (*participants who live more than 75-miles away and can attend study visits at NCCH or virtually remain eligible for participation*).
- 3.2.3. Unwilling to be audio-recorded during facilitated study visits and feedback interview.

## **4.0 STUDY PLAN**

### **4.1 Schema**

This is a non-randomized, single-arm psychosocial intervention pilot study of 10 patient-co-parent dyads (N=20). Dyads will participate in 2-3 study visits with an intervention facilitator and receive psychoeducation materials. Study visits will occur at NCCH, in participants' homes, or virtually via video conferencing when an in-person visit is not feasible. Home study visits will only be offered to participants who live within 75 miles of NCCH. We anticipate enrolling participants over a 18-month period (extended due to COVID-19) and that active participation will last for a three-month period.

#### **4.2 Duration of Study**

Expected duration of study participation is three months.

Baseline assessment (T0): We anticipate the pre-study visit assessment to last approximately 30 minutes.

Study visit 1 (T1): The first study visit consists of the first meeting with the intervention facilitator and the study visit assessments. The intervention facilitator meeting is expected to last 60-120 minutes. The study visit assessments are anticipated to take 30 minutes. If possible, visits will be scheduled two weeks apart; however, given the variable stamina of participants, participants will be given a seven-week period (five-week tolerance, from time of meeting with intervention facilitator to time of next study visit) to complete the study visit assessments.

Study visit 2 (T2): The second study visit consists of the second meeting with the intervention facilitator and the study visit assessments. The intervention facilitator meeting is expected to last 60-120 minutes. The study visit assessments are anticipated to take 30 minutes. If possible, visits will be scheduled two weeks apart; however, given the variable stamina of participants, participants will be given a seven-week period (five-week tolerance, from time of meeting with intervention facilitator to time of next study visit) to complete the study visit assessments.

Study visit 3 (T3): The optional third study visit consists of a third meeting with the intervention facilitator and the study visit assessments for participant dyads who elect to pursue a third study visit with the intervention facilitator. The intervention facilitator meeting is expected to last 60-120 minutes. The study visit assessments are anticipated to take 30 minutes. If possible, visits will be scheduled two weeks apart; however, given the variable stamina of participants, participants will be given a seven-week period (five-week tolerance) to complete the study visit assessments.

Post-intervention assessment (T4): The post-intervention assessment consists of a telephone or in-person interview with each participant to provide feedback on the intervention. The interview is expected to last 30-45 minutes. If possible, post-intervention assessments will be conducted within two weeks of the last intervention visit; however, given the variable stamina of participants, participants will be given a seven-week period (five-week tolerance) to complete the post-intervention interview.

Follow-up assessment 1 (T5): Chart abstraction will be performed by the study team 6 months after the dyad's most recent intervention study visit, with a two-week tolerance. Participants may choose to participate in an optional additional follow-up interview at this time.

Follow-up assessment 2 (T6): Chart abstraction will be performed by the study team 12 months after the dyad's most recent intervention study visit, with a two-week tolerance.

#### 4.3 Study Details

##### Pre-study Assessments

###### Screening

The RA or PI will identify eligible patients through the UNC multidisciplinary breast conference and review of the outpatient five-day breast oncology clinic schedules. The study team will maintain a screening log that outlines whether screened patients meet eligibility criteria.

###### Screen failures

Screen failures are defined as participants who consent to participate in this study but are not subsequently assigned to the study intervention or entered in the study. This may include participants whose physical or cognitive functioning worsens and interferes with their ability to engage in study activities; participants who die from their disease in the period between study enrollment and the first study visit; and participants who are lost to follow-up (i.e., do not respond to attempts to schedule first study visit).

###### Recruitment and informed consent:

*The study team has conducted multiple prior studies with the target patient population and is highly experienced with respect to approaching eligible patients and clinic recruitment. Hundreds of advanced cancer patients who are parents have participated in the study team's prior research studies and the study team has demonstrated the ability to discuss sensitive topics such as parenting and advanced cancer in a manner that is acceptable to patients and their families.*

UNC clinic recruitment will occur with the cooperation of the clinic attendings. A member of the study team will confirm the patient's eligibility and receive permission from the patient's oncologist or advanced practice provider before approaching any eligible patient.

We will request that the patient's oncology provider first introduce the study purpose and study team member to potential participants using a brief recruitment script (see Appendix A). The study team member will then discuss the study with the eligible patient and provide information about the study (see Appendix B for recruitment brochure), allowing ample time for questions. The study team member will obtain written or verbal informed consent from all patients before enrollment. For patients receiving healthcare from the PI as their provider, the PI (instead of or in addition to an oncology provider) may pursue verbal confirmation of the patient's willingness to be contacted by other members of the study team for recruitment purposes.

This is a dyadic study and therefore requires both the patient and her co-parent to enroll for participation to occur. If the potential participant's co-parent is willing to participate in the study and is also present during initial recruitment then written informed consent will also be obtained at the same time as the patient. If the co-parent is not present at the time of patient enrollment then the study team will offer the following recruitment strategies for the co-parent of the consenting patient:

- (1) Have the patient introduce the study to the co-parent with a study brochure and copy of the consent form for the co-parent followed by a phone call from the study team. If the co-parent is willing to participate in the study then the study team member will obtain verbal consent from him/her.
- (2) If the co-parent is expected to attend a future oncology-related appointment with the patient, the study team will also offer to approach the co-parent in person at that visit.

In the event that a dyad would like to participate but the patient did not provide written consent at the time of initial in-person recruitment, both patient and co-parent may provide verbal consent over the phone. Both members of the dyad will sign additional written consents at the next available opportunity or meeting with study personnel. This will reduce participation burden in the event that a dyad or individual participant wishes to participate but wishes to discuss the study with their partner or family, would like additional time to consider participation, or for other reasons. This ensures that participants will not be caused unnecessary delay in scheduling study visits or collection of baseline measures.

All attempts will be made to recruit potential participants in person, and to obtain written informed consent. In circumstances where this is not feasible due to participant convenience, burden, or COVID-19 restrictions, potential participants may be recruited by email or telephone. This will only occur after the patient has verbally confirmed with the oncology provider that the study team may contact them. Participants who are unable to provide written consent for the above reasons may provide verbal consent to the study. In this circumstance, patient participants will provide electronic HIPAA consent via secure Qualtrics link, and all participants will provide additional written documentation of consent via Qualtrics link. All consent forms will be emailed to participants who wish to retain copies for their records. In the event that a participant consents verbally but

attends a study visit in person at a later date, additional written consents will be obtained at that time. Verbal consent is appropriate for the risk profile of this intervention.

### **Baseline study assessment**

After receiving consent from both the patient and the co-parent, the study team member will obtain baseline assessment information from the participant dyad. Participants can complete the study forms online via a secure Qualtrics or RedCAP link, by pen and paper, or via telephone. The baseline study assessment consists of a demographic form and several patient/co-parent outcome measures (see Appendix C for copies of measures). See the study measures section for details about the measures and how they will be administered to the participants. Baseline assessments must be completed before the first study visit.

### **Study visits**

During the study visits, the patient and co-parent participate together as a dyad with the intervention facilitator. The standard intervention will include Study Visits 1 and 2. Study Visit 3 is optional and will be offered to participant dyads who wish to have a third session with the intervention facilitator. Study visits will consist of two parts: (1) a face-to-face meeting with the intervention facilitator, and (2) data collection with the research assistant.

We will schedule study visits at the convenience of the participants. The participants will be provided with a choice regarding study visit location. The study visits will be conducted in either: (1) a clinical patient care area of the NCCH, (2) the participants' home (if they live within a 75-mile radius of NCCH), or (3) virtually via video conferencing if an in-person visit is not feasible. If participants request to participate in a home-based study visit then the intervention facilitator will travel with another member of the study team.

Participants will be provided a five-week interval to complete study visit assessments. The assessment window begins immediately after completing the face-to-face meeting with the intervention facilitator until five weeks after the study visit or immediately before participating in their next study visit – whichever time point occurs first. Participants can complete study assessments via an online Qualtrics link, via hard copy, or via telephone.

The intervention facilitator will be the PI or a trained licensed clinical social worker with experience providing clinical care to oncology and palliative medicine patient populations. The intervention facilitator will conduct the study visit in accordance with the study manual (see Appendix D for Intervention Facilitator manual) and patient education materials (see Appendix E for patient education materials) and will prepare a written memo after each study visit with participant dyads. The study visits with the intervention facilitator will be audio-recorded and professionally transcribed to aid with treatment fidelity monitoring and qualitative analyses.

*Of note, the development of the intervention manual, training materials, and patient education materials have been extensively and iteratively reviewed by a panel of patient, caregiver, and healthcare provider stakeholders who have found the materials to be acceptable and emotionally sensitive. In addition, the intervention manual has several “branch” points in which questions and materials are offered to participants based on their stated willingness to acknowledge the severity of their illness and discuss sensitive topics. As such, the risk that the intervention content will cause undesired or unanticipated emotional distress to participants is reduced.*

*The intervention facilitator will be either the PI (a psychiatrist with expertise in psycho-oncology and 8 years of direct clinical experience with the target patient population) or a licensed clinical social worker supervised by the PI. The social worker will be a clinical member of the UNC Comprehensive Cancer Support Program and thus will have direct experience working with advanced cancer patients. He/she will undergo a minimum of two days of intervention training by the PI, involving self-study, role play, practice interviews, and demonstration of core competencies. In addition, the intervention will be supervised by the PI throughout the study and re-training to the social worker will be offered if large deviations from the intervention manual or other concerns arise during the course of the study. The PI has developed a comprehensive training manual to facilitate this.*

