### **Contact between or after study visits**

Participants will be offered phone access to the intervention facilitator between or after study visits if they develop new or intervening concerns. The intervention facilitator will offer to connect participants with available resources and answer targeted questions but will not engage in formal psychotherapeutic counseling during these contacts. The number and reason for participants' contact with the intervention facilitator will be logged and evaluated at the end of the study.

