## ADEQUACY OF PROTECTION AGAINST RISKS

**Recruitment and informed consent.** Eligible participants will be identified through conversation with oncology attendings and review of the outpatient five-day breast oncology clinic schedules. The RA or PI will receive permission from the patient's oncologist or advance practice provider before approaching any eligible patient. As such, participants for whom the treating oncology provider believes are at high risk of emotional distress from study participation will not be approached. The RA and PI will approach eligible patients about enrollment in the UNC Breast Clinic and we will ask each potential patient participant for consent. In the event that in-person recruitment is not feasible (such as COVID-19 restrictions), initial recruitment contacts may occur by email or telephone. Potential participants may only be contacted by email or telephone for recruitment after they have verbally confirmed with their oncology provider that they are willing to be contacted by the study team. For patients receiving healthcare from the PI as their provider, the PI (instead of or in addition to an oncology provider) may pursue verbal confirmation of the patient's willingness to be contacted by other members of the study team for recruitment purposes.

We will make all attempts to obtain written informed consent from participants when possible. Written informed consent will be obtained by the PI or other member of the study team for eligible participants who receive services at NC Cancer Hospital. Copies will be given to participants and kept locked in the study team's office. The PI or RA will obtain verbal consent from participants who do not receive services at NC Cancer Hospital before enrollment, or when in-person consent is not feasible (due to participant burden, convenience, or COVID-19 restrictions). Patient participants providing verbal consent will provide HIPAA consent electronically through a secure Qualtrics link, and will additionally provide documentation of adult consent via Qualtrics link. Participants will be emailed copies of all consent forms for their records if desired.

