To protect against the risk of emotional distress the RA will describe the nature of the study questions and their purposes during initial participant recruitment. We will also take the following additional measures to reduce the risk of emotional distress that may occur in some study participants. First, the RA or PI will receive permission from the patient's oncologist or nurse practitioner before approaching any eligible UNC patients. As such, participants who the treating oncology provider believes are at high risk of emotional distress from study participation will not be approached. Second, adverse events during or between study visits such as the unlikely eventuality of severe emotional distress (including suicidality) will be reported to the IRB by the PI—a board-certified psychiatrist with specialized training in psycho-oncology, and if the participant is a patient at UNC—her primary oncologist will be notified; if the participant such affected is the co-parent, then his/her primary care physician or practitioner (if available) will be notified by the PI. Should study staff observe emotional reactions necessitating clinical intervention, the study participant will be provided immediate support services in the form of psycho-oncology assessment by a trained member of the UNC Comprehensive Cancer Support Program (CCSP) psycho-oncology service (which the PI oversees). If the participant already receives CCSP services, we will also contact the participant's CCSP provider if severe emotional distress is noted during study visits.

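### The PI may deliver the study sessions to the PI's own patients, and the plan neither avoids nor records this in a study whose primary outcome is acceptability

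*Combined protocol and SAP*

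**What the plan says.** On delivery, section 4.3 (Study visits) states: "The intervention facilitator will be the PI or a trained licensed clinical social worker". It later describes the PI's profession: "The intervention facilitator will be either the PI (a psychiatrist with expertise in psycho-oncology". Of the alternative facilitator it says: "The social worker will be a clinical member of the UNC Comprehensive Cancer Support Program".

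On who may enrol, section 4.3 (Recruitment and informed consent) has a provision that begins "For patients receiving healthcare from the PI as their provider". Section 4.4 (Adequacy of Protection Against Risks) repeats it: "For patients receiving healthcare from the PI as their provider, the PI (instead of or in addition to an oncology provider) may pursue". In both places the PI may ask whether such a patient agrees to be approached, and the approach itself is then made by someone else on the team. The provision is limited to recruitment.

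Section 4.4 also provides for participants already under the care of the cancer support program (CCSP), in a sentence that begins "If the participant already receives CCSP services". It refers to that program's "psycho-oncology service (which the PI oversees").

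On the outcome, section 2.1 makes acceptability the primary objective and bases it on satisfaction ratings and interviews from patients and co-parents. Section 4.3 (Satisfaction assessment) describes a 13-item questionnaire plus one overall item on a 5-point scale, which asks about the visit. Section 7.3 has the ratings collected after each visit and the interviews analysed thematically. Sections 4.1 and 7.2 give the design: a single arm with 10 dyads, 20 participants in all.

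**The concern.** A patient who rates sessions run by her own psychiatrist is rating two things: the manualised intervention, and a relationship that existed before the study and may continue after it. Goodwill, and some reluctance to criticise a clinician she still relies on, both push towards favourable answers. The overall satisfaction item asks about the visit, so it cannot tell the two apart.

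The pilot's results are meant to refine the intervention for a later randomised trial against usual care. If some of the acceptability comes from existing psycho-oncology care, that should be visible when the results are read. The plan recognises the dual role when a patient is first approached but does not carry the safeguard through to the sessions.

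**Working it through.** The plan gives no figure to reproduce: section 7.2 justifies the sample size as adequate for qualitative work, not by a formula. The check is therefore a comparison of provisions, followed by an illustration of size.

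**Can the overlap occur under the plan as written?**

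1. The PI's patients may enrol: yes, provided for in sections 4.3 and 4.4.
2. The PI may be the facilitator: yes, section 4.3.
3. A treatment relationship is an exclusion: no. Section 3.2 lists inability to take part, distance or refusal of virtual visits, and refusal of audio-recording. Section 3.1 has no such criterion either.
4. There is a rule for assigning facilitators to dyads: none in section 4.3.
5. The relationship is recorded, or results are shown by facilitator or relationship: not specified in sections 4.3 or 7.3.

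Items 1 and 2 together permit the overlap. Items 3 to 5 show that nothing in the available text prevents it or would let an analyst identify it.

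**The social worker.** The social worker belongs to CCSP and participants may already use CCSP, so the same overlap is possible. No section says that the study social worker treats any participant. This route is an inference; the PI route rests on the text.

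**Illustration of size.** Let *k* be the number of patients whose facilitator already treats them, and *d* the rise in their overall rating due to that relationship. The documents give neither. Assume *k* = 1 to 3 and *d* = 1 point on the 5-point item, complete ratings, and no effect on co-parents.

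- Shift in the mean over 10 patients = *k* × *d* / 10. For *k* = 1: 1 × 1 / 10 = 0.1. For *k* = 3: 3 × 1 / 10 = 0.3.
- Shift in the mean over all 20 raters = *k* × *d* / 20. For *k* = 1: 1 / 20 = 0.05. For *k* = 3: 3 / 20 = 0.15.
- With *d* = 0.5, each figure halves: 0.05 to 0.15 over patients, 0.025 to 0.075 over all raters.
- With *k* = 0, the shift is zero.

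**The case against.** The strongest reply is that this is a small formative pilot with several protections already in place. Primary acceptability is assessed mainly by qualitative methods, and the input sought in section 7.3 (relevance, format, language, sensitivity) is mostly about content and not about the facilitator. The research assistant collects the visit data. Patient and co-parent complete measures and interviews separately. Section 7.3 adds triangulation between the two sources, member checking and an audit trail. No satisfaction threshold is set, so no stated decision turns on a shift of the size illustrated. The facilitator manual (Appendix D) is not in the available text and could contain an assignment rule.

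Much of this stands and keeps the point modest. It does not remove it. Independent data collection eases pressure at the moment of rating, but not the effect of a prior relationship on the experience being rated. Triangulation helps only if the analyst knows which dyads are concerned. The PI may also conduct the post-intervention interview and takes part in coding, so independence at those later steps is not assured.

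A reader might infer more than the documents support:

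- **That enrolment of the PI's patients is expected.** The provisions are conditional. They allow it and do not predict it.
- **That the limit on between-visit contact breaks down.** The statement that the facilitator "will not engage in formal psychotherapeutic counseling during these contacts" concerns study phone contacts, so an ordinary clinical appointment does not breach it. The wording on logging contacts with the facilitator does not exclude clinical ones.
- **That the change scores are compromised.** Section 7.3 already calls that analysis exploratory and unpowered, and in a single-arm study usual care is mixed with the intervention whoever provides it.
- **That the ratings say nothing about acceptability.** Only dyads with such a relationship are affected, and for them only in part.

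**Conclusion.** The concern holds in a conditional form. As written, the plan lets the PI deliver sessions to the PI's own patients, and the available text neither avoids nor records this. For any such dyad, the patient's contribution to the primary outcome is partly a response to an existing treatment relationship, probably favourable. With a single arm and 10 dyads, the two influences cannot be separated later unless the relationship is recorded.

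The size is unknown and could be nil. Under the assumptions stated (1 to 3 patients, 1 point each), the overall satisfaction mean would rise by 0.1 to 0.3 among patients. Over all 20 raters the rise would be 0.05 to 0.15 if co-parents have no such relationship. These figures show scale and do not estimate bias. The extension to the CCSP social worker is possible but inferred. The conclusion assumes that the unseen facilitator manual contains no assignment rule.

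**What to change.** Add to section 4.3 (Study visits):

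> Where possible, a dyad is assigned to the facilitator (PI or social worker) who has no current or past treatment relationship with either member. Any such relationship is recorded at enrolment, and where it could not be avoided, that dyad's satisfaction ratings and interview themes are also shown separately.

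If Appendix D already holds such a rule, refer to it in section 4.3 and add the recording and separate display.

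The cost is these two sentences and one field on the enrolment form. No dyad is excluded, and both facilitator roles are already named. The downside is less freedom in scheduling, and the social worker may take more sessions. The plan does not establish that both facilitators will always be available; if only one is, the recording and separate display still apply. The change is partial: the PI would still supervise the social worker, review session recordings and take part in coding. With so few dyads, the separate display is descriptive only and needs care not to identify participants.
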